8.22 Reports will be submitted to: IRB, FDA (MedWatch)

8.3 Data Monitoring Committee (if applicable)
Not applicable

9.0 CLINICAL AND LABORATORY EVALUATIONS AND STUDY CALENDAR

See Appendix A

10.0 CRITERIA FOR EVALUATION AND ENDPOINT DEFINITIONS

The outcome status (in terms of toxicity, response, reason off study, progression, and survival) of all eligible patients will be reported. All eligible patients who begin treatment will be included in the analysis of survival and time-to-failure.

Endpoint Definitions

11.0 SPECIAL INSTRUCTIONS:

Blood samples will be obtained at the following time points after the third dose of each dosage form: 0 (predose), 0.5, 1, 2, 3, 4, 8, 24, and 48 hours postdose.

In the case where the patient is discharged home early, we will offer subjects the option of having a trained healthcare professional come to the subject's home to perform the 24 hour and 48 hour blood and sputum sampling. A phleobomist not affiliated with USC will come to the subject's home to collect the 24 hour and/or 48 hour blood and sputum sample.

In order for the study visit to be conducted in the subject's home, the subject's name, address and contact telephone number will be provided to the home provider vendor. The home provider vendor will provide the information to a courier, who will pick up the blood and sputum from the subject's home. If you do not want your information provided to the home provider vendor or courier, the subject cannot participate in the home visit.

It is possible that the home provider vendor may not be available in the subject's area or in time for the study visit. In this rare event, the subject will be required to complete the study visit at the study doctor's office.

Expectorated sputum samples will be obtained from individual patients after the third dose of each dosage form as follows:

Patients	Time of sputum collection
1-12	Predose
1-3	0.5-1h
4-6	2h
7-9	3h
10-12	4h

1-4	8h
5-8	24h
9-12	48h

Blood and sputum samples will be processed and stored at -80°C until assayed for tedizolid.

12.0 DATA COLLECTION AND MONITORING

Data will be collected on case report forms, which will be retained for the duration of the study. Data will include subject demographics, clinical characteristics, laboratory data, and results of pharmacokinetic analyses. Data will be coded and stored on a password protected electronic database.

13.0 DATA/STATISTICAL CONSIDERATIONS

13.1 Pharmacokinetic analysis

Pharmacokinetics will be performed using standard noncompartmental methods. The maximum concentration and time to maximum concentration will be from the observed data. The area under the curve will be calculated using the trapezoidal rule. Absolute bioavailability will be determined by a ratio of the AUC_{po}/AUC_{iv}.

In addition, population pharmacokinetic analysis will be performed using the maximum likelihood estimation via the EM algorithm with sampling (MLEM) as implemented in ADAPT 5 (Biomedical Simulations Resource, University of Southern California). Multiple candidate models will be evaluated to identify the model that best describes the observed plasma and sputum concentration data.

Monte Carlo simulations will be performed to determine the target attainment for the lung exposures (sputum AUC_{24h}/MIC > 20) with different dosing regimens using the SIM module in ADAPT 5. MIC distributions used in the simulations will be based on recently published susceptibility data [29].

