1.0 BACKGROUND AND HYPOTHESES

Cystic fibrosis (CF) is a genetic disorder characterized by a chronic cycle of airway infection, obstruction, and inflammation leading to progressive loss of lung function and eventual respiratory failure. Over the past decade the prevalence of infections involving *Methicillin Resistant Staphyococcus Auerus* (MRSA) in CF has increased dramatically.[1] Importantly, recent epidemiological studies have demonstrated that the presence of MRSA in the airways of patients with CF is associated with more rapid lung function decline [2] and a higher mortality [3]. Management of these patients includes prompt initiation of antibiotics at the onset of acute pulmonary exacerbations. A significant barrier to effective treatment is the limited number of safe and effective antibiotics for treatment of MRSA pulmonary infections. While vancomycin has been the mainstay of treatment for many years, its efficacy is limited by reduced susceptibility. In addition, the risk for acute kidney injury is significant in patients with CF due to the concomitant use of tobramycin for treatment of coinfection with *Pseudomonas aeruginosa*. While linezolid has demonstrated to be efficacious in the treatment of acute pulmonary exacerbations in CF, its use is significantly limited due to the high prevalence of depression (29-46%), which is often treated with selective serotonin reuptake inhibitors/serotonin non-epinephrine reuptake inhibitors(SSRIs/SNRIs) [4]. Tedizolid offers a significant advancement in the management of infections involving MRSA in CF due to its excellent activity, penetration into pulmonary secretions, proven safety, and reduced potential for drug interactions with antidepressants.

The pharmacokinetics of a number of medications has shown to be altered in patients with CF. [5,6] In general, patients with CF demonstrate an increased volume of distribution when expressed in liter/kilogram (L/Kg) of body weight, and increased renal clearance. In addition, the oral bioavailability of lipophilic medications is reduced due to pancreatic insufficiency. To our knowledge no study has evaluated the pharmacokinetics of tedizolid in patients with CF. The proposed study is designed to characterize the pharmacokinetics of intravenous and oral tedizolid in patients with CF and determine the optimal dosing regimen in preparation for future efficacy and safety studies in CF patients experiencing acute pulmonary exacerbations.

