3.0 STUDY DESIGN

This study will be conducted using a prospective multiple dose, crossover design to characterize the steady-state pharmacokinetics of tedizolid intravenous/oral (IV/PO) in CF. A total of 12 adult patients with CF will participate in the study and will receive tedizolid 200mg IV or PO once daily for 3 doses followed by a minimum 2 day washout and receipt of the remaining dosage form.

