13.2 Statistical Analysis

Twelve patients with CF will participate in this study. The endpoints for this study are descriptive in nature and the sample size is similar to other studies with these endpoints. Patient demographics, clinical characteristics, and pharmacokinetic parameters will be summarized using descriptive statistics.

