Appendix I: Informed Consent
Appendix II: Study Calendar

	Screening	Day 1	Day 2	Day 3	Day 4	Day 5	Day 6-10	Day 7-11	Day 8-12	Day 9-13	Day 10-14
Informed Consent	X										
Medical History	X										
Medication History	X										
Height, weight	X										
Vital signs ^A	X	X	X	X	X	X	X	X	X	X	X
Safety labs ^B	X										
IV drug administration ^Q		X ^C	X ^C	X ^C			X ^F	X ^F	X ^F		
PO drug administration		X ^E	X ^E	X ^E			X ^D	X ^D	X ^D		
Blood Pharmacokinetics (PK) ^G				X					X		
Sputum Pharmacokinetics (PK): pre dose ^H				X							
Sputum PK: 0.5 to 1 hour post dose				X ^I					X ^I		
SputumPK: 2 hours post dose				X ^J					X ^J		
SputumPK: 3 hours post dose				X ^K					X ^K		
SputumPK: 4 hours post dose				X ^L					X ^L		
SputumPK: 8 hours post dose				X ^M					X ^M		

SputumPK:Q 24 hours post dose					X ^O					X ^O	
SputumPK:Q 48 hours post dose						X ^P					X ^P

- A. Vital signs to include blood pressure, heart rate, temperature, respiratory rate.
- B. Safety labs to include complete blood count with differential, complete metabolic panel
- C. For the treatment arm A: IV Tedizolid will be done on days 1 to 3.
- D. For the treatment arm A: PO Tedizolid will be done on days 10 to 12. Days 10 and 11 the dose of oral Tedizolid will be done at home for the subject. A telephone call will be done to remind the subject to take the PO Tedizolid.
- E. For the treatment arm B: PO Tedizolid will be done on days 1 to 3. Days 1 and 2 can be done at home. A telephone call will be done to remind the subject to take the PO Tedizolid.
- F. For the treatment arm B: IV Tedizolid will be done on days 10 to 12.
- G. All subjects will have a pre dose blood PK levels, 0.5 hour, 1, 2, 3, 4, 8, 24 and 48 hours post dose of Tedizolid (IV or PO). A 5mL EDTA tube will be used to collect the blood PK sample.
- H. All subjects will have a pre dose sputum sample (IV or PO).
- I. Subject number 1-3 will need to produce a sputum sample at this time period (IV or PO).
- J. Subject number 4-6 will need to produce a sputum sample at this time period (IV or PO).
- K. Subject number 7-9 will need to produce a sputum sample at this time period (IV or PO).
- L. Subject number 10-12 will need to produce a sputum sample at this time period (IV or PO).
- M. Subject number 1-4 will need to produce a sputum sample at this time period (IV or PO).
- N. Subject number 5-8 will need to produce a sputum sample at this time period (IV or PO).

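### Section 13.1 does not say which trapezoidal rule is used across the 8-24 h plasma gap; read as linear, AUC(0-24) is overstated by about 3-11% IV and 2-11% PO (assumed half-life 6-14 h, oral ka 0.5-2 per h)

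*Combined protocol and SAP*

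**What the plan says.** Section 13.1 places the plasma analysis within a general framework, "Pharmacokinetics will be performed using standard noncompartmental methods", and then states that "The area under the curve will be calculated using the trapezoidal rule". It names no trapezoidal variant, no software setting and no interval for the plasma AUC. The one use it gives for this AUC is the PO/IV ratio for absolute bioavailability. Sputum target attainment is assigned to the population model and Monte Carlo simulation.

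Section 11.0 sets blood sampling after the third dose of each dosage form at "0 (predose), 0.5, 1, 2, 3, 4, 8, 24, and 48 hours postdose". Note G of the study calendar (Appendix II) gives the same times, "0.5 hour, 1, 2, 3, 4, 8, 24 and 48 hours post dose of Tedizolid (IV or PO"). No plasma sample falls between 8 and 24 h.

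Section 3.0 gives the aim as "to characterize the steady-state pharmacokinetics of tedizolid intravenous/oral (IV/PO) in CF". Section 13.2 says that "pharmacokinetic parameters will be summarized using descriptive statistics".

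**The concern.** Both the linear rule and linear-up/log-down are standard, so the framework sentence does not choose between them. With dense sampling the choice hardly matters. Here a single segment covers two thirds of the dosing interval. A straight line between two points on an exponential decline lies above the curve, whereas a log-down segment follows it.

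The reported plasma AUC is at stake. The error is systematic, so averaging over 12 patients does not remove it, and it grows as elimination gets faster. A reader who is not told the variant also cannot reproduce the AUC or compare it with other studies.

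The missing interval is a smaller gap. AUC(0-24) is the natural reading for once-daily dosing at steady state, but sampling runs to 48 h and 13.1 does not say.

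**Working it through.** **Inputs from the documents.** 200 mg once daily for three doses, IV over 1 h or PO (section 7.1). Plasma after dose 3 at 0, 0.5, 1, 2, 3, 4, 8 and 24 h (section 11.0, calendar note G).

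**Assumptions not in the documents.** Half-life 6-14 h; one compartment; first-order oral absorption with ka 0.5-2 per h, and 0.3 per h as a slow case. The documents state no AUC or half-life, so there is no figure of the plan's own to reproduce.

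**Step 1: the 8-24 h segment alone.** For an exponential decline with rate k = ln 2 / half-life, put x = 16k. The ratio of the straight-line area to the true area is

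R = (x/2)(1 + e^-x)/(1 - e^-x).

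- Half-life 6 h: x = 1.848, e^-x = 0.1575, R = 0.924 × 1.1575/0.8425 = 1.270, or +27%.
- Half-life 14 h: x = 0.792, e^-x = 0.453, R = 0.396 × 1.453/0.547 = 1.052, or +5%.

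**Step 2: effect on IV AUC(0-24).** At half-life 6 h with unit infusion rate and volume, the third-dose concentrations are C(8) = 0.4486 and C(24) = 0.0707.

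- Linear area, 8-24 h: 16 × (0.4486 + 0.0707)/2 = 4.154.
- True area, 8-24 h: 0.4486 × (1 - 0.1575)/0.1155 = 3.272.
- True AUC(0-24): 8.654.
- Contribution of this segment: (4.154 - 3.272)/8.654 = 10.2 points, out of a total linear error of 10.7%.

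**Step 3: all segments, compared with fine-grid integration of the third-dose AUC(0-24).**

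| Half-life (h) | IV linear | IV log-down | PO linear, ka 0.5 / 1 / 2 | PO log-down, ka 0.5 / 1 / 2 |
|---|---|---|---|---|
| 6 | +10.7% | 0.0% | +10.0 / +10.6 / +10.0% | -1.8 / -0.7 / -0.7% |
| 8 | +7.2% | 0.0% | +6.2 / +7.0 / +6.7% | -1.4 / -0.5 / -0.5% |
| 10 | +5.1% | 0.0% | +4.1 / +4.8 / +4.7% | -1.2 / -0.4 / -0.4% |
| 12 | +3.8% | 0.0% | +2.8 / +3.5 / +3.4% | -1.0 / -0.4 / -0.3% |
| 14 | +2.9% | 0.0% | +2.0 / +2.6 / +2.6% | -0.9 / -0.3 / -0.3% |

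**Step 4: sensitivity.**

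- *Slow absorption, ka 0.3.* PO linear error is +6.5% at half-life 6 h, falling to +0.2% at 14 h. Log-down is -3.9 to -2.2%. At half-life 10-14 h the linear rule is then the closer of the two (+1.6 to +0.2% against -2.8 to -2.2%).
- *Two-compartment IV, distribution half-life 0.5-2 h carrying 10-30% of the AUC.* Linear error is +3.4 to +12.6%; log-down is +0.4 to +3.1%.

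**Step 5: bioavailability.** Relative to the true AUC ratio over the same interval, with ka 0.5-2, AUCpo/AUCiv is 0.990-0.999 with the linear rule and 0.982-0.997 with log-down. The largest gap is about 1.2 points, at ka 0.5 and half-life 6 h (0.994 against 0.982).

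**Step 6: third dose against full steady state.** The third-dose IV AUC(0-24) falls short of the steady-state value by 1.6% at half-life 12 h and 2.9% at 14 h. Dose/AUC compared with true clearance is then:

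| Half-life (h) | Linear | Log-down |
|---|---|---|
| 6 | -9.6% | +0.05% |
| 8 | -6.5% | +0.2% |
| 10 | -4.2% | +0.7% |
| 12 | -2.1% | +1.6% |
| 14 | +0.1% | +3.0% |

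**The case against.** The plan is silent rather than wrong. Its framework sentence allows log-down, and under log-down the one-compartment IV error vanishes. That stands: no bias is built into the plan, only into one reading of it.

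The only stated use of this AUC is the PO/IV ratio. There the error nearly cancels, and log-down is equal or up to about 1.2 points worse for ka 0.5-2. The objectives in section 2.0 are steady-state concentrations and target attainment, and target attainment comes from the population model and simulation. This stands too. What remains is a descriptive AUC with no test attached.

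The sizes rest on a half-life and an absorption rate that the documents do not give. That also stands, which is why they are shown as ranges. An IV error above 7.2% needs a half-life below 8 h.

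A reader might go further and infer that the study would understate clearance, masking the "of body weight, and increased renal clearance" that section 1.0 describes in CF. The documents do not support this. Section 13.1 derives no clearance. Section 1.0 speaks of CF patients in general and says that, to the authors' knowledge, tedizolid pharmacokinetics have not been studied in CF. Step 6 also shows that at half-life 14 h dose/AUC from the linear rule is almost unbiased, while log-down is 3.0% off. At about 12-14 h the linear PO value likewise lies closer to the steady-state AUC (at ka 1 and 14 h, -0.4% against -3.3%), but only because two opposite errors offset each other. This does not make the linear rule a better estimate of the third-dose AUC(0-24).

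**Conclusion.** The point holds as a minor, cheap improvement. The trapezoidal variant is unstated, and the sampling schedule makes the choice visible in the result. If the linear rule is applied, third-dose plasma AUC(0-24) is overstated by about 3-11% for IV and about 2-11% for PO. This assumes half-life 6-14 h, one compartment and ka 0.5-2 per h; at ka 0.3 the PO range is +0.2 to +6.5%. Log-down on the same samples brings this to about 0% for IV and -0.3 to -1.8% for PO.

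The benefit is confined to the reported plasma AUC. It should not be read as a flaw in the bioavailability estimate, the population model or target attainment, nor as a finding about clearance.

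**What to change.** Add one sentence to section 13.1: plasma AUC is AUC(0-24) after dose 3, calculated by the linear-up/log-down trapezoidal rule on actual sample times, over the same interval for IV and PO.

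The cost is that sentence and a software setting, with no new samples. There are three downsides to accept. PO AUC will be slightly low, and by 2.2 to 3.9% if absorption is as slow as ka 0.3. A distribution phase would leave a small positive error in the IV value. At a long half-life neither rule corrects for dose 3 falling short of steady state, so the result should be labelled as the third-dose AUC(0-24).

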13.2 Statistical Analysis

Twelve patients with CF will participate in this study. The endpoints for this study are descriptive in nature and the sample size is similar to other studies with these endpoints. Patient demographics, clinical characteristics, and pharmacokinetic parameters will be summarized using descriptive statistics.

14.0 REGISTRATION GUIDELINE

14.1 Subjects will be registered into the study through submission of the research order form, informed consent, and patient bill of rights to the Clinical Trials Office (CTO) at USC..

15.0 BIOHAZARD COMTAINMENT

Not applicable

16.0 ETHICAL AND REGULATORY CONSIDERATIONS

All institutional and Federal regulations concerning the Informed Consent form will be fulfilled. The study will be conducted in adherence to ICH Good Clinical Practice.

Appendix I: Informed Consent
Appendix II: Study Calendar

	Screening	Day 1	Day 2	Day 3	Day 4	Day 5	Day 6-10	Day 7-11	Day 8-12	Day 9-13	Day 10-14
Informed Consent	X										
Medical History	X										
Medication History	X										
Height, weight	X										
Vital signs ^A	X	X	X	X	X	X	X	X	X	X	X
Safety labs ^B	X										
IV drug administration ^Q		X ^C	X ^C	X ^C			X ^F	X ^F	X ^F		
PO drug administration		X ^E	X ^E	X ^E			X ^D	X ^D	X ^D		
Blood Pharmacokinetics (PK) ^G				X					X		
Sputum Pharmacokinetics (PK): pre dose ^H				X							
Sputum PK: 0.5 to 1 hour post dose				X ^I					X ^I		
SputumPK: 2 hours post dose				X ^J					X ^J		
SputumPK: 3 hours post dose				X ^K					X ^K		
SputumPK: 4 hours post dose				X ^L					X ^L		
SputumPK: 8 hours post dose				X ^M					X ^M		

SputumPK:Q 24 hours post dose					X ^O					X ^O	
SputumPK:Q 48 hours post dose						X ^P					X ^P

- A. Vital signs to include blood pressure, heart rate, temperature, respiratory rate.
- B. Safety labs to include complete blood count with differential, complete metabolic panel
- C. For the treatment arm A: IV Tedizolid will be done on days 1 to 3.
- D. For the treatment arm A: PO Tedizolid will be done on days 10 to 12. Days 10 and 11 the dose of oral Tedizolid will be done at home for the subject. A telephone call will be done to remind the subject to take the PO Tedizolid.
- E. For the treatment arm B: PO Tedizolid will be done on days 1 to 3. Days 1 and 2 can be done at home. A telephone call will be done to remind the subject to take the PO Tedizolid.
- F. For the treatment arm B: IV Tedizolid will be done on days 10 to 12.
- G. All subjects will have a pre dose blood PK levels, 0.5 hour, 1, 2, 3, 4, 8, 24 and 48 hours post dose of Tedizolid (IV or PO). A 5mL EDTA tube will be used to collect the blood PK sample.
- H. All subjects will have a pre dose sputum sample (IV or PO).
- I. Subject number 1-3 will need to produce a sputum sample at this time period (IV or PO).
- J. Subject number 4-6 will need to produce a sputum sample at this time period (IV or PO).
- K. Subject number 7-9 will need to produce a sputum sample at this time period (IV or PO).
- L. Subject number 10-12 will need to produce a sputum sample at this time period (IV or PO).
- M. Subject number 1-4 will need to produce a sputum sample at this time period (IV or PO).
- N. Subject number 5-8 will need to produce a sputum sample at this time period (IV or PO).
- O. Subject number 9-12 will need to produce a sputum sample at this time period (IV or PO).
- P. IV Tedizolid is be infused over 60 minutes.
- Q. The option of home health vendor to collect the 24 and 48 hour blood and sputum sampling.

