RATIONALE FOR SPUTUM TEDIZOLID CONCENTRATIONS:

Determination of the pulmonary penetration of antibiotics is vital to predicting the optimal dosing regimen for treatment of lung infections. Several different sampling methods are reported in the literature including bronchoalveolar lavage and induced or expectorated sputum. The choice of sampling technique is dependent upon multiple factors such as the site of infection, convenience, and need for serial samples. Cystic fibrosis is characterized by chronic respiratory infection/inflammation that leads to airway remodeling and progressive loss of lung function. The site of the infection/inflammation is predominately endobronchial rather than alveolar. This is consistent with the location of Cystic Fibrosis Transmembrane conductance regulator (CFTR) within the submucosal glands and acinar serous cells of the airways. Therefore, the ideal sample for drug concentrations would be from the endobronchial space which is best obtained by induced or expectorated sputum. Fiberoptic bronchoscopy, being invasive and costly, is poorly suited for serial sampling of airway secretions. In addition, bronchoscopy with lavage is thought primarily to sample the alveolar space rather than the airways alone. Numerous publications including those from our group have utilized expectorated sputum to successfully characterize the disposition of various antibiotics within the airways and determine optimal dosing regimens for treatment of airway infections in CF.²³⁻²⁸

Our study hypothesis is that tedizolid will exhibit excellent oral bioavailability and sputum penetration in patients with cystic fibrosis.

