2.0 OBJECTIVES AND PURPOSE

Primary Objective:

Determine the steady-state concentrations of tedizolid in plasma and sputum of patients with CF.

Secondary Objective:

Determine the target attainment for the pharmacodynamic endpoint.

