6.0 STRATIFICATION/DESCRIPTIVE FACTORS/RANDOMIZATION SCHEME

6.1 Stratification factors: Not applicable.

6.2 Descriptive factors: Not applicable.

6.3 Randomization:

Randomization sequence will be created using Excel 2007 (Microsoft, Redmond, WA, USA) with a 1:1 allocation using random block sizes of 2.

Subjects will be randomized to receive one of the two treatment sequences:

Oral Tedizolid for days 1 to 3 then Intravenous Tedizolid for days 10 to 12.

Intravenous Tedizolid for days 1 to 3 then Oral Tedizolid for days 10 to 12.

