8.12 CBC and CMP will be monitored at baseline

8.2 Adverse Event Reporting:

8.21 Any significant adverse events that occurs during the course of the study will be documented and reported.

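### Do unobserved home oral doses, with no listed record of dose times, undermine the bioavailability ratio and the steady-state profile?

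*Combined protocol and SAP*

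**What the plan says.** Appendix II, footnote D, fixes home dosing for the first two oral doses in arm A (IV first): "Days 10 and 11 the dose of oral Tedizolid will be done at home for the subject". Footnote E makes it optional in arm B (oral first): "Days 1 and 2 can be done at home". Both footnotes add: "A telephone call will be done to remind the subject to take the PO Tedizolid".

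Footnote G sets the plasma schedule: "All subjects will have a pre dose blood PK levels, 0.5 hour, 1, 2, 3, 4, 8, 24 and 48 hours post dose". Section 11.0 places these samples after the third dose of each form.

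Section 2.0 gives the primary objective: "Determine the steady-state concentrations of tedizolid in plasma and sputum of patients with CF". The hypothesis closing Section 1.0 is that "tedizolid will exhibit excellent oral bioavailability and sputum penetration in patients with cystic fibrosis". Section 13.1 computes AUC by the trapezoidal rule and takes absolute bioavailability as AUCpo over AUCiv. It names no AUC interval and no correction for drug left from earlier doses. It also plans a population model in ADAPT 5, followed by target-attainment simulations.

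Section 12.0 says data go on case report forms and lists demographic, clinical and laboratory data and the pharmacokinetic results. Dose times are not in that list. Section 13.2 calls the endpoints descriptive, with 12 patients.

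**The concern.** A reminder call prompts a dose; it does not record whether or when the dose was taken. Because sampling is around dose 3 only, the oral AUC includes whatever remains of doses 1 and 2. If dose 2 was missed, that residue is too small and F reads low. If it was taken late, the residue is too large and F reads high. The IV doses are not assigned to the home in this way, so the error would not cancel in the ratio.

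The same patient's profile would also not be the steady-state profile that the primary objective describes. A population fit that assumed nominal dose times would pass the error on to the simulations. Dose times not noted when the dose is taken may be hard to recover later.

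**Working it through.** **Inputs.** From the documents: 200 mg by each route, three doses 24 h apart; plasma at 0, 0.5, 1, 2, 3, 4, 8, 24 and 48 h around dose 3; trapezoidal AUC; F = AUCpo/AUCiv; N = 12. The documents give no half-life, miss rate or delay, and no calculated figure to reproduce. Assumed: linear one-compartment kinetics, half-life 6, 8 or 12 h, absorption rate 0.5 to 2 per h, IV doses on time.

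**Step 1: does the ratio need a carry-over correction?** Let r be the fraction of drug left after 24 h, so r = 0.5^(24/half-life): 0.0625, 0.125 and 0.25 at 6, 8 and 12 h. With three doses on time, AUC(0-24) after dose 3 is proportional to 1 + r + r² by either route, once absorption is complete. The factor cancels in the ratio. A numerical run at the planned sampling times gives F = 0.989 to 0.999 for a true value of 1. The stated estimator is sound when doses are taken as planned.

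**Step 2: dose 2 missed.** The oral AUC changes by the factor (1 + r²)/(1 + r + r²).

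| Half-life | Calculation | Change in that patient's F |
|---|---|---|
| 6 h | 1.0039/1.0664 = 0.941 | -5.9% |
| 8 h | 1.0156/1.1406 = 0.890 | -11.0% |
| 12 h | 1.0625/1.3125 = 0.810 | -19.0% |

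With first-order absorption and the planned sampling times, the range is -6.2 to -21.8%. AUC(0-48) gives -6.2 to -21.1%, so leaving the interval unstated hardly matters here.

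**Step 3: dose 2 mistimed.** With the same numerical model, 4 h late gives +3.7 to +5.7%, 12 h late +18.7 to +24.4%, and 4 h early -2.3 to -4.5%. A delay of 1 to 2 h gives only about +0.8 to +2.7%.

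**Step 4: effect on the mean of 12.** One patient with dose 2 missed: -6.2/12 = -0.5% to -21.8/12 = -1.8%. One patient 12 h late: 18.7/12 = +1.6% to 24.4/12 = +2.0%. With an assumed 20% error per sample, the SD of log F is about 0.15, so the standard error is at least 0.15/√12 = 0.043. If patients also vary by 15 to 25%, it is √(0.15² + 0.15²)/√12 = 0.061 to √(0.15² + 0.25²)/√12 = 0.084. One affected patient therefore moves the mean by less than half a standard error on any of these figures.

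**Step 5: would the scheduled samples show it?** The ratio of predose to 24 h concentration should be (1 + r)/(1 + r + r²), which is 0.95 to 1.00. With dose 2 missed it is r/(1 + r²), which is 0.06 to 0.24. A missed dose 2 stands out plainly. A dose 4 h late gives 1.10 to 1.50, which sampling error can hide.

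**Step 6: would a routine correction help?** Subtracting the residue returns F to 0.98 to 1.03 in these scenarios. At a 12 h half-life, however, it raises the SD of log F from about 0.15 to 0.24-0.25, about 2.5 times the variance. As a standing rule for patients who dosed correctly, it would cost precision for no gain.

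**The case for a change.** The strongest opposing case is that the predose sample cannot reliably reveal a late dose, so only recorded times can; that a habit shared by several patients does not average out; and that a time field costs almost nothing. If all 12 took dose 2 four hours late, mean F would rise by 3.7 to 5.7%. If only the six in arm A did (Section 6.3 allocates "with a 1:1 allocation using random block sizes of 2"), the rise would be 1.8 to 2.8%. Each post-dose sputum time also has only 3 or 4 patients. If sputum followed plasma, a 22% error in one of three would move that mean by about 7%.

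The arithmetic stands, and recording home dose times is good practice. The rest is weaker:

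- The shared habit is hypothetical, and even for all 12 patients it amounts to about one standard error or less once patients are allowed to vary. No comparison between sequences is planned that it could distort.
- The absence of a record is not established. The Section 12.0 list is not exhaustive: it omits adverse events, yet Section 8.21 says "Any significant adverse events that occurs during the course of the study will be documented and reported". The calendar marks oral drug administration on each oral dosing day and vital signs on every study day. Neither proves that times are kept, but both suggest contact beyond a call.
- Section 13.1 nowhere says nominal times will be used. No size can be put on that harm, because the planned population fit was not simulated.
- Footnote E permits home dosing but does not require it. Section 5.1 uses admission as an entry condition, and Section 11.0 foresees early discharge. These passages can be read together.

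The predose check has its own limit. The 24 h sample may be drawn at home and off time. A rule that queries predose/24 h ratios below 0.5 would wrongly query about 1% of correct periods at exactly 24 h, but 3 to 5% if the draw were at 22 h. It should be read with actual draw times.

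**Conclusion.** No change to the plan is needed. The stated ratio is right when doses are taken as planned, and no printed rule yields a wrong result. What remains is that the protocol prints no field for home dose times, a detail that may sit in the case report form and that anyone fitting a population model has to obtain anyway.

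The consequence for one patient can be material: about -6 to -22% for a missed dose 2 and about +4 to +6% for a 4 h delay. For the mean of 12 it is about 2% or less per affected patient. F supports the hypothesis but is not among the objectives in Section 2.0, and the endpoints are descriptive.

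These sizes rest on an assumed half-life of 6 to 12 h and one-compartment kinetics. At 16 h, a missed dose 2 would give 1.125/1.479 = 0.761, or about -24% for that patient and about -2.3% on the geometric mean of 12. That does not alter the conclusion.
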